While early detection and removal of colorectal adenoma by screening colonoscopy with polypectomy reduce CRC incidence and mortality, interval cancers (cancers that develop after a colonoscopy and before the next scheduled colonoscopy) may still occur and were reported to account for up to 10.5% of CRC [8-9]. The protective effect of colonoscopy against cancer in the right colon has not been consistently demonstrated [9-12]. Interval CRC has been associated with proximal colon location, small lesion, flat lesion, missed lesion, inadequate examination, incomplete resection of lesion, tumor biology, and low adenoma detection rate (ADR) [12-15].

High ADR (eg, $\geq 20\%$) has been associated with a reduced risk of interval CRC [14,15]. Methods that can improve polyp detection in the right colon such as retroflexed examination of the right colon, second forward view examination of the right colon, use of colonic fold flattening device, colonoscope with an increased field of view may potentially reduce the risk of interval CRC, but data is still limited [16-20]. Performance of a second forward view (SFV) examination of the right colon may be the easiest and safest from a practical standpoint when compared to other options (eg, additional training is often needed for retroflexed examination of the right colon since there may be a potentially higher risk of perforation in endoscopists not familiar with the technique, additional equipment is needed when using a colonic fold flattening device, or a colonoscope with an increased field of view). In a recent randomized control study comparing retroflexed examination and SFV examination in the right colon in patients undergoing screening or surveillance colonoscopy, high ADRs were achieved by both methods (47% in retroflexed group vs 46% in SFV group, $p = 0.75$) [17]. A recent single arm prospective cohort study of 280 male veteran patients in USA showed that additional adenomas were detected in 15.4% of the patients after a SFV examination of the right colon [18]. The overall ADR increased by 3.2% and the ADR for the right colon increased by 6.7% after SFV examination of the right colon [18]. 3.6% of the patients had a change in their screening / surveillance interval with the addition of findings on the SFV examination of the right colon [18]. Of note, the overall ADR in this cohort of male veteran patients was very high and up to 71.8% on conventional withdrawal exam [18]. It is unclear whether a SFV examination of the right colon would still be beneficial in populations with both males and females and a lower overall ADR (eg, closer to the

recommended colonoscopy quality indicator of an ADR of 20% by the American Society of Gastrointestinal Endoscopy). To date, there has been no dedicated randomized controlled study comparing the yield of SFV examination in the right colon to that of conventional withdrawal examination of the right colon on adenoma /polyp detection in patients undergoing screening and surveillance colonoscopies. Our current study aims to determine whether a routine SFV examination in the right colon can lead to an increase in adenoma / polyp detection when compared to conventional withdrawal examination in the right colon in both male and female patients undergoing screening and surveillance colonoscopies.

HYPOTHESIS

Performance of a SFV examination in the right colon can increase adenoma / polyp detection when compared to conventional withdrawal examination of the right colon in patients undergoing screening and surveillance colonoscopies.

AIM

To investigate the impact of a SFV examination in the right colon on the right-sided and overall adenoma / polyp detection in patients undergoing screening and surveillance colonoscopies in a randomized controlled study.

METHODOLOGY

Study Design

It is an international multi-centre randomized controlled study

Setting

Endoscopy centers in Prince of Wales Hospital, combined endoscopy unit in Alice Ho Miu Ling Nethersole Hospital, and partner institutes of Asia-Pacific Working Group on Colorectal Cancer.

Study Population

The study protocol, risks and benefits of procedures, and informed consent would be discussed either in a pre-colonoscopy clinic visit or on the day of scheduled colonoscopy procedure at two endoscopy centres in Prince of Wales Hospital and combined endoscopy unit in Alice Ho Miu Ling Nethersole Hospital, and partner institutes of Asia-Pacific Working Group on Colorectal Cancer based on the local institutional guidelines. After informed consent form is signed by the patient, patient will be enrolled into the study, with study randomization conducted on the day of procedure (see endoscopic procedure description below).

Eligibility

Inclusion Criteria

- Patients undergoing colonoscopy for CRC screening or polyp surveillance
- Age 50 - 75 years
- Written informed consent available

Exclusion Criteria

- Contraindications for endoscopy due to comorbidities
- Unable to provide written informed consent
- Personal history of prior resection of any portion of the colon, familial polyposis syndrome, inflammatory bowel disease
- Patients with incomplete colonoscopy (i.e, inability to achieve cecal intubation), a Boston Bowel Preparation Scale (BBPS) score of 0 in either right colon, transverse colon, or left colon at the time of colonoscopy
- Known history of coagulopathy and thrombocytopenia
- Pregnant patients

Study Flow

Patients who fulfill inclusion criteria and sign informed consent form for the study will be assessed for the followings:

- Demographics: age, gender, height, weight
- Clinical Conditions: indication for colonoscopy, family history of CRC, personal history of colonic polyp, history of prior CRC screening, comorbidities (eg, diabetes, etc), smoking history, use of antiplatelets and antithrombotic medications

Standard colonoscopy will be performed. The only intervention in the study is the SFV in the right colon. The additional risk of SFV should be minimal and similar to standard colonoscopy since it does not involve a new endoscopic skill or new equipment. Patients' vital signs will be monitored during colonoscopy. Data such as cecal intubation time, total procedure withdrawal time, the size, morphology, and location of each polyp, bowel preparation quality assessment by BBPS, additional withdrawal time for the SFV in the right colon, presence of immediate complications such as perforation, bleeding, hypotension, etc and final histology of the removed polyps will be collected.

After colonoscopy, patients will be monitored for any immediate complications. If no sign of immediate complication is detected, patient will be discharged according to standard discharge protocol for sedated procedure. Oral intake will be resumed with diet advancement as tolerated after discharge. Patients will be given a designated telephone line for post-colonoscopy adverse events reporting and follow up during office hours within 30 days. They will be instructed to attend the nearby Accident and Emergency Department for serious adverse events out of office hours. All information about post-colonoscopy serious adverse events will be retrieved from hospital record system on day 30.

Patients will be followed up at their original clinic after colonoscopy. The interval for next screening or surveillance colonoscopy will be determined based on findings of colonoscopy, number and histology of polyp removed during colonoscopy, patient's clinical and family history accordingly to regional and international guidelines [5]. This follow up is not the study procedure but standard care.

Endoscopic Procedures

Colonoscopy will be performed by investigators in their standard sessions. Olympus (Tokyo, Japan) high definition colonoscopes will be used in this study. Narrow band imaging (NBI), an image enhanced function on the endoscope, may be used for characterization of an identified polyp at the discretion of the endoscopist but not routinely for polyp detection during entire examination. In addition, chromoendoscopy can be used when sessile serrated adenoma is suspected. Conscious sedation with intravenous administration of midazolam and pethidine would be used during the procedure with regular monitoring of vital signs. A digital rectal (PR) examination will be performed before insertion of the endoscope. The colonoscope will be passed to cecum. A colonoscopy would be considered incomplete if cecal intubation cannot be achieved. Distal attachment (also known as a cap or hood) would not be used routinely during colonoscopy to enhance colonic fold flattening / exposure.

Standard Colonoscopy Procedure (Conventional group)

The colonoscope will then be withdrawn from the cecum with irrigation and aspiration of any residual colonic contents for careful examination of the colonic mucosa for polyps. During the initial colonoscope withdrawal from cecum to hepatic flexure (ie, the first forward view examination of the right colon), polyps detected in the right colon (ie, cecum and ascending colon) will be removed and sent for histopathological examination. Once the colonoscope is withdrawn to the level of hepatic flexure, patients will be randomized to either a SFV examination of the right colon, or continuation of the conventional colonoscopy withdrawal for examination of colonic mucosa for polyps. In the conventional group, colonoscope withdrawal will be continued from hepatic flexure to rectum after randomization. Examination of colonic mucosa for polyps from hepatic flexure to rectum will be performed per standard of care. Polyps detected in these areas will be removed and sent for histopathological examination accordingly. Risks of colonoscopy such as perforation, bleeding, or infection were reported to be less than 1%.

Second Forward View Colonoscopy Procedure (SFV group)

During the initial colonoscope withdrawal from cecum to hepatic flexure (ie, the first forward view examination of the right colon), polyps detected in the right colon (ie, cecum and ascending colon) will be removed and sent for histopathological examination. Once the colonoscope is withdrawn to the level of hepatic flexure, patients will be randomized to either a SFV examination of the right colon, or continuation of the conventional colonoscopy withdrawal for examination of colonic mucosa for polyps. For the SFV group, the colonoscope will be advanced to the cecum again when hepatic flexure was reached the first time, where a SFV examination of the right colon will be

performed. Additional polyps removed in the right colon during the SFV examination will be sent for histopathological examination in separate specimen containers to avoid being confused with the polyps removed during the first forward view examination of the right colon. Examination of colonic mucosa for polyps from hepatic flexure to rectum will follow standard practice.

The risk of harm or discomfort of the second forward view examination of the right colon is similar to the risks of standard colonoscopy (less than 1% chance of perforation, bleeding, etc) because it does not involve a new endoscopic skill or new equipment. Based on local data at the Prince of Wales Hospital, the second forward view examination of right colon takes about an additional 2 minutes. No additional sedation medication was needed for the added time based on the local data.

Randomization Method

Block randomization generated by a computer program will be used at study site. Randomization will be in 1:1 ratio.

OUTCOME MEASURES

Primary Outcomes

- 1) Per-patient ADR in the right colon in each group. For the SFV group, it is defined as the number of patients with at least 1 adenoma identified in the right colon on either the first or second examination of the right colon divided by the total number of patients in the SFV group. Thus, if a patient has at least 1 adenoma detected on both the first examination and the second examination of the right colon, then this patient will be counted once only. For the conventional group, it is defined as the number of patients with at least 1 adenoma identified in the right colon on the conventional withdrawal examination of the right colon divided by the total number of patients in the conventional withdrawal group.

Secondary Outcomes

- 1) Increase in per-patient ADR in the right colon in the SFV group.
 - It is defined as the difference between the new ADR in the right colon after the first examination and SFV (again, if a patient has at least 1 adenoma detected on both the first examination and the second examination of the right colon, then this patient will be counted once only) and the ADR in the right colon after the first examination.
- 2) Overall ADR for the entire colon in each group.
 - For the SFV group, it is defined as the number of patients with at least 1 adenoma identified on either the second examination of the right colon or on the first examination of the right + examination from hepatic flexure to rectum, divided by the total number of patients in the SFV group. Thus, if a patient has at least 1 adenoma detected on both the first examination and

the second examination of the right colon, then this patient will be counted once only. For the conventional group, it is defined as the number of patients with at least 1 adenoma identified in the whole colon on the conventional withdrawal examination divided by the total number of patients in the conventional withdrawal group.

[figure not shown]
- 3) The number of patients with at least 1 additional adenoma detected in right colon in the SFV group
- 4) Adverse events during colonoscopy and up to 30 days post colonoscopy (eg, perforation, bleeding, etc)
- 5) Total number of adenomas found on the first and second examinations of the right colon in the SFV group, and that on the examination of the right colon in the conventional group
- 6) Total number of polyps (all pathological type) found on the first and second examinations of the right colon in the SFV group, and that on the examination of the right colon in the conventional group

Bowel preparation quality assessment:

Endoscopists will rate the quality of bowel preparation using the Boston bowel preparation scale (BBPS), a quantitative scale that assesses bowel preparation after all cleansing maneuvers are completed by the endoscopist [21]. A 4-point scoring system will be used to rate the following three main regions of the colon: right colon (ie, cecum, ascending colon), transverse colon (ie, hepatic flexure, transverse colon, splenic flexure), and left colon (ie, descending colon, sigmoid, rectum).

Figure 1: A, Segment score 0, unprepared colon segment with mucosa not seen because of solid stool that cannot be cleared. B, Segment score 1, portion of mucosa of the colon segment seen, but other areas of the colon segment not well seen because of staining, residual stool, and/or opaque liquid. C, Segment score 2, minor amount of residual staining, small fragments of stool and/or opaque liquid, but mucosa of colon segment seen well. D, Segment score 3, entire mucosa of colon segment seen well with no residual staining, small fragments of stool and/or opaque liquid [21]. Therefore, the maximum BBPS score for a perfectly clean colon without any residual liquid is 9, and the minimum BBPS score for an unprepared colon is 0.

Figure 1: (reference 21)

SAMPLE SIZE CALCULATION

Based on an ADR in the right colon of 16.0% from a screening colonoscopy cohort in Hong Kong, and assuming a SFV examination of the right colon would give a 6.7% increase in ADR in the right colon [18], we would need 502 patients per study group (ie, a total of 1004 patients for the study) in order to give a power of 80% at a type 1 error of 5%.

STATISTICAL ANALYSIS

Categorical variables will be analyzed using chi-square test or Fisher's exact test. Continuous variables will be analyzed using Student's t-test or Mann-Whitney U test. $P < 0.05$ is considered to be statistically significant.

TIME TABLE OF WORK

The ethics committee's approval of the study will be sought. The study will commence in November / December 2016 upon ethics committee's approval. The expected project duration is 24 months.

DATA HANDLING AND DISSEMINATION OF INFORMATION

All data obtained from the study will be kept confidential and be available only to personnel involved in the study and patient care. Case report forms and other documents will be kept in designated area of the Institute of Digestive Disease and retained for 7 years after study completion. The results of this study will be presented in scientific meetings and medical journals.

DISCLOSURE

The study would be conducted in compliance with the Declaration of Helsinki.

REFERENCE

1. World Health Organization. International Agency for Research in Cancer. Globocan 2012: estimated cancer incidence, mortality and prevalence worldwide 2012.
2. Hong Kong Cancer Registry. Leading Cancer Sites in Hong Kong in 2013, Hong Kong: Hospital Authority. Retrieved on 1st August 2016 from http://www3.ha.org.hk/cancereg/rank_2013.pdf

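### If randomisation is blocked within site, a site-stratified test of right-colon ADR would gain a little power at no measurable cost; the planned pooled test is valid (low severity)

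*Combined protocol and SAP*

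**What the plan says.** - Study Design: "It is an international multi-centre randomized controlled study". The Setting section names two Hong Kong centres and "partner institutes of Asia-Pacific Working Group on Colorectal Cancer". The number of sites and the patients per site are not given.
- Randomization Method: "Block randomization generated by a computer program will be used at study site" and "Randomization will be in 1:1 ratio". Block size is not given, and the text does not say outright whether each site has its own list.
- Primary Outcomes: right-colon ADR is the number of patients with at least one adenoma, "divided by the total number of patients in the SFV group", and correspondingly for the conventional group. This defines the endpoint on whole-group totals. It does not by itself prescribe an unstratified test.
- Statistical Analysis: chi-square or Fisher's exact for categorical variables, with P below 0.05 as the threshold. No stratified test, site covariate or other centre adjustment appears anywhere in the document.
- Sample Size Calculation: "Based on an ADR in the right colon of 16.0% from a screening colonoscopy cohort in Hong Kong", with a gain of 6.7 (read here as percentage points), 502 patients per group, 80% power and 5% type I error.

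**The concern.** Blocking within site keeps the two groups balanced at every site, so differences in ADR between sites cannot contribute to the treatment comparison. A pooled chi-square test still counts that between-site variation in its standard error. The standard error is then slightly too large, the true type I error falls a little below 5%, and some power is given up. A test stratified by the randomisation stratum recovers it.

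Differences between sites are plausible: several countries, different endoscopists, and an entry criterion ("Patients undergoing colonoscopy for CRC screening or polyp surveillance") whose mix of screening and surveillance could vary by centre. They are not documented. What is at stake is a small amount of efficiency, and having the role of site in the primary comparison settled before the data are seen.

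**Working it through.** **1. The plan's own figure.** Inputs from the Sample Size Calculation section: p1 = 0.160, p2 = 0.160 + 0.067 = 0.227, mean 0.1935. Two-sided 5% is assumed, as the section does not state sidedness.

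n per group = [1.960·√(2·0.1935·0.8065) + 0.8416·√(0.160·0.840 + 0.227·0.773)]² / 0.067² = 544.5, so 545.

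The stated 502 is not reproduced. It is reproduced exactly if 22.7% is rounded up to 23%. Power at 502 per group:

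Φ[(0.067·√502 − 1.0950) / 0.5567] = Φ(0.7297) = 76.7%.

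This is a separate matter. It is shown because it sets the baseline for what follows.

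**2. What ignoring site does under per-site blocking.** Let τ² be the variance of control ADR between equal-sized sites. The pooled test uses a null variance proportional to 0.16·0.84 = 0.1344, while the true one is 0.1344 − τ². Its type I error is therefore 2·[1 − Φ(1.960 / √(1 − τ²/0.1344))]. For power, with the same 6.7-point gain at every site:

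- pooled: Φ[(1.5012 − 1.960·√0.3121) / √(0.3099 − 2τ²)]
- stratified: Φ[(1.5012 − 1.960·√(0.3121 − 2τ²)) / √(0.3099 − 2τ²)]

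Here 1.5012 = 0.067·√502, 0.3121 = 2·0.1935·0.8065, and 0.3099 = 0.160·0.840 + 0.227·0.773.

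The site ADRs below are assumptions; each set averages 16.0%.

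| Control ADR at four sites | SD (points) | τ² | Pooled type I error | Pooled power | Stratified power | Gain (points) |
|---|---|---|---|---|---|---|
| 16/16/16/16% | 0 | 0 | 5.0% | 76.7% | 76.7% | 0 |
| 10/14/18/22% | 4.5 | 0.00200 | 4.8% | 76.9% | 77.3% | 0.4 |
| 8/13/18/25% | 6.3 | 0.00395 | 4.7% | 77.0% | 77.8% | 0.8 |
| 5/10/20/29% | 9.2 | 0.00855 | 4.3% | 77.4% | 79.0% | 1.7 |

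**3. Simulation of the same scenarios.** 200,000 trials each, 502 per group, balanced within site; Pearson chi-square against Cochran-Mantel-Haenszel (CMH) without continuity correction. Power, pooled against stratified: 77.0/77.0%, 77.2/77.6%, 77.3/78.1% and 77.7/79.4%. Pooled type I error was 5.0, 4.8, 4.7 and 4.2%; CMH stayed at 4.9 to 5.1%. Simulated power runs up to about 0.4 points above the formula, but the gains agree.

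**4. Does stratifying cost anything under per-site blocking?** With equal ADR at every site and 4, 10, 20 or 50 sites, power was 76.9/76.8/76.9/76.7% pooled and 76.9/76.8/76.9/76.8% stratified. With incomplete final blocks (block size 4 assumed) the two differed by 0.05 points or less. No loss is measurable.

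**5. If one list covers all sites.** With equal sites, pooled against stratified: 76.7% against 76.4% (10 sites), 76.9% against 76.1% (20) and 77.1% against 74.9% (50). The loss is 0.3, 0.8 and 2.2 points.

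**The case against.** The strongest reply is that nothing here is wrong. The pooled test never exceeds 5% type I error in these scenarios, so the plan can be followed as written and gives a valid answer. That stands, and it is why the point is of low severity.

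The benefit is also small. Going from 76.7% to 80% power takes 545 − 502 = 43 patients per group, about 0.077 points each (3.3/43). A gain of 0.4 to 0.8 points is thus worth some 5 to 10 patients per group. It is nil if sites are alike, and every site spread used is an assumption. All of this stands.

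The premise is a reading, too. The phrase about study site could merely say where allocation takes place, since patients are randomised mid-procedure at the hepatic flexure. Under a single list, stratifying by many small sites loses power. A gain would remain possible with few, very different sites (four sites from 8% to 24%: 76.8% pooled, 77.6% stratified), but the documents give no number of sites on which to plan that. The recommendation is therefore confined to per-site blocking.

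Three stronger readings are tempting and are not supported:
- *The pooled test is invalid or inflates false positives.* The calculation shows the opposite direction.
- *Stratifying restores the stated 80% power.* None of the four-site scenarios reaches it. Two equal sites at 4% and 28% would (78.0% pooled, 80.8% stratified), but that is fewer sites than the Setting section describes.
- *The documents show that site ADRs differ.* The 20% benchmark and the 71.8% in one veteran cohort, both in the background, are overall ADRs outside this trial and not rates at its sites.

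**Conclusion.** The point holds as a low-severity, cost-free improvement. On the most natural reading of the randomisation section, the primary test ignores the stratum by which patients are allocated. The consequence is slight conservatism (type I error 4.7 to 4.8% for moderate spreads, 4.2 to 4.3% at the extreme) and a power gain forgone of 0, about 0.4 to 0.8, or about 2 points as assumed site differences go from none to moderate to extreme.

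This rests on per-site lists, roughly equal sites, a control ADR averaging 16.0%, a constant 6.7-point gain and 502 per group. The documents supply only the 16.0%, the 6.7 and the 502. The shortfall from 80% to about 77% power is separate and remains whichever test is used.

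**What to change.** In the Statistical Analysis section, state that right-colon ADR (primary) and overall ADR are compared between groups with a Cochran-Mantel-Haenszel test stratified by study site, the randomisation stratum, and reported with a Mantel-Haenszel risk difference and 95% CI. Fix the merging rule before analysis, and merge only sites too small to be informative. Merging sites with different ADRs gives the gain back: with 20 sites (SD 4.5 points) combined into five mixed strata, stratified power fell from 77.5% to 77.1%, the same as pooled.

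In the Randomization Method section, add a sentence confirming that lists are blocked separately by site. If the sponsor confirms instead that one list covers all sites, keep the pooled test.

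The cost is one sentence in each of two sections, plus a site variable in the dataset. The data items listed under Study Flow do not name site, but it is known for every patient. No extra patients or procedures are needed.

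### Secondary outcome 1 is a paired, nested difference within the SFV arm, but the only categorical tests the plan names assume independent groups

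*Combined protocol and SAP*

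**What the plan says.** Under Outcome Measures, the first secondary outcome is "Increase in per-patient ADR in the right colon in the SFV group". The text beneath that title makes it a subtraction of two rates, with each patient counted once: "difference between the new ADR in the right colon after the first examination and SFV" is the opening of the definition, and what is taken away is the rate found on the first look alone. Both rates belong to the SFV arm and share its denominator. The description of the SFV procedure confirms that each of these patients has a first look at the right colon and then a second.

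The Statistical Analysis section is three sentences long. For categorical data it states: "Categorical variables will be analyzed using chi-square test", with Fisher's exact test as the alternative. For continuous data it names Student's t-test or Mann-Whitney U, and it sets the threshold at P < 0.05. It makes no exception for any outcome and mentions no paired test, one-sample method or confidence interval.

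Secondary outcome 3 is a related count in the same arm: "The number of patients with at least 1 additional adenoma detected in right colon in the SFV group".

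**The concern.** Chi-square and Fisher's exact tests, used to compare two rates, treat them as coming from separate sets of patients. That suits the primary outcome, which compares the randomized arms. It does not suit this outcome, where one set of patients supplies both rates and the first-look positives are a subset of the combined positives.

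The shared positives make the two rates strongly correlated. Ignoring that correlation inflates the standard error and the p value. A gain observed directly, patient by patient, could then be reported as not significant, or with an interval too wide to use. This is the outcome that measures most directly what the second look adds.

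**Working it through.** **Inputs.** From Sample Size Calculation: first-look right-colon ADR 16.0%, gain 6.7 points (hence 22.7% after both looks), n = 502 per arm. The plan gives no figure for secondary outcome 1, so there is none to reproduce. I take 502 as stated; the ratio of standard errors below does not depend on n.

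**1. The increase is one proportion.** Let p1 be the first-look rate, p2 the rate after both looks, and d = p2 − p1. Because first-look positives are all combined positives, no patient can move from positive to negative, and d is the share positive only on the second look.

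The covariance of the two indicators is p1 − p1·p2 = p1(1 − p2), so the paired variance is

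[p1(1 − p1) + p2(1 − p2) − 2·p1(1 − p2)] / n = [0.1344 + 0.1755 − 0.2474] / 502 = 0.0625 / 502.

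This equals d(1 − d)/n = 0.067 × 0.933 / 502, the variance of a single proportion.

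**2. Standard errors at the planning values.**
- Treated as independent: √[(0.16 × 0.84 + 0.227 × 0.773) / 502] = 0.0248
- As one proportion: √[0.067 × 0.933 / 502] = 0.0112
- Ratio: 2.2

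The ratio depends on the gain and the base rate:

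| Base | Gain (points) | Ratio |
|---|---|---|
| 16% | 3 | 3.15 |
| 16% | 4 | 2.77 |
| 16% | 5 | 2.51 |
| 16% | 6.7 | 2.23 |
| 16% | 8.8 | 2.00 |
| 16% | 10 | 1.91 |
| 11.5% | 6.7 | 2.00 |
| 10% | 6.7 | 1.91 |

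**3. What each method would report.** Take 80 first-look positives out of 502 (16.0% of 502 is 80.3) and k patients gained. Chi-square (uncorrected) and Fisher compare 80/502 with (80 + k)/502 as if independent. The exact interval is Clopper-Pearson for k/502. The last column is d ± 1.96 × the independent-groups standard error.

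| k | Gain (points) | Chi-square p | Fisher p | Exact 95% CI | Independent-groups 95% CI |
|---|---|---|---|---|---|
| 16 | 3.2 | 0.18 | 0.21 | 1.8 to 5.1 | −1.5 to 7.9 |
| 20 | 4.0 | 0.100 | 0.118 | 2.5 to 6.1 | −0.8 to 8.7 |
| 24 | 4.8 | 0.0503 | 0.060 | 3.1 to 7.0 | 0.0 to 9.6 |
| 25 | 5.0 | 0.042 | 0.0505 | 3.2 to 7.3 | 0.2 to 9.8 |
| 34 | 6.8 | 0.007 | 0.008 | 4.7 to 9.3 | 1.9 to 11.6 |

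So chi-square first reaches p < 0.05 at 25 patients gained and Fisher at 26. At 16 or 20 gained, the independent-groups interval includes negative values, which this outcome cannot take.

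**4. How often it would matter.** I simulated the SFV arm as a three-category multinomial (positive on first look, positive only on second, never positive) with a 16% base and n = 502. Chi-square gave p < 0.05 in about 96%, 57% and 19% of trials for true gains of 6.7, 5 and 4 points.

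**The case against.** The plan never says that this outcome will be tested. A difference between two rates in one arm can fairly be read as descriptive, in which case the categorical rule does not reach it and the defect is an unstated method, not a wrong one. At the only effect size the plan gives, the conclusion would not change: p is 0.007 or 0.008, and about 96% of simulated trials are significant. The error is conservative, so it cannot create a false claim of benefit. The plan names no interval for any outcome, so the independent-groups interval is an inference about what might be built. Nothing is lost irretrievably, because the correct proportion can be computed at the reporting stage.

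Much of this stands and limits the weight of the point. It does not remove it. The rule is general, carries a significance threshold and has no alternative beside it, so an analyst who follows the text reaches the wrong test. If the outcome is meant to be descriptive, the plan should say so and name an interval. Gains of 5 points or less are not stated in the plan, but they are realistic. The 6.7 points come from an all-male veteran cohort with an overall ADR of 71.8% on conventional withdrawal, and the background text itself doubts whether the benefit carries over to populations with a lower ADR.

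**Conclusion.** The concern holds. Secondary outcome 1 is a single proportion in one arm, and the plan's only rule for categorical variables does not fit it. If that rule is applied, the standard error is overstated 2.2-fold at the planning values, and by more for smaller gains. The planned gain would still be significant, but with 80 first-look positives chi-square would miss any gain of up to 24 patients (4.8 points), and Fisher up to 25 (5.0 points).

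These figures assume a 16% first-look rate and all 502 SFV patients analysed; gains other than 6.7 points are illustrative. The primary outcome, the other between-arm comparisons and the sample size are unaffected. This should be corrected, but it does not threaten the trial's main conclusion.

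**What to change.** Add to Statistical Analysis: *Secondary outcome 1 is exempt from the chi-square/Fisher rule. It will be reported as the proportion of SFV patients with no right-colon adenoma on the first examination and one or more on the second, among all SFV patients, with an exact (Clopper-Pearson) or Wilson 95% confidence interval.* Choose one of the two interval methods before analysis. At 34/502 they differ little: 4.7 to 9.3 exact, 4.9 to 9.3 Wilson. No test against zero is needed, because the gain cannot be negative; replacing chi-square with McNemar's test would add little.

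Report secondary outcome 3 with the same interval method, and state that it is a different proportion, because as worded it also counts patients already positive on the first look. The cited cohort shows the gap: "additional adenomas were detected in 15.4% of the patients after a SFV examination of the right colon", whereas "the ADR for the right colon increased by 6.7% after SFV examination of the right colon". If those rates carried over to 502 patients, which is only an assumption, they would be about 77 patients (0.154 × 502 = 77.3; exact CI 12.3% to 18.8%) and 34 patients (0.067 × 502 = 33.6; 4.7% to 9.3%).

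The cost is one or two sentences. No new data are needed, because second-look polyps already go to histology "in separate specimen containers to avoid being confused with the polyps removed during the first forward view examination of the right colon".
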